6.2 Dabrafenib + Trametinib Dose Modifications

The table below outlines the dose levels to be used for any necessary dabrafenib and trametinib dose modifications in studies which include the combination:

Current Dose Dabrafenib	If Dose Reduction Required	Reduce To
150mg BID	→	150 mg QAM, 75 mg QPM
150 mg QAM, 75 mg QPM	→	75mg BID
75mg BID	→	Discontinue dabrafenib

Current Dose Trametinib	If Dose Reduction Required	Reduce To
2mg QD	→	1.5mg QD
1.5mg QD	→	1.0mg QD
1.0mg QD	→	Discontinue trametinib

If an AE resolves to grade 1 or baseline at the reduced dose level, and no additional toxicities are seen after 4 weeks of study treatment at the reduced dose, the dose may be increased to the previous dose level. A dose reduction below 75 mg BID for dabrafenib and 1 mg once daily for trametinib is not allowed. If a dose reduction below 75 mg BID is required, dabrafenib will be permanently discontinued, but the patients will be allowed to continue trametinib. If a dose reduction below 1.0 mg once daily for trametinib is required, then trametinib will be permanently discontinued, but these patients will be allowed to continue pembrolizumab and/or dabrafenib.

The dose modifications may involve one or both agents, and should be based on the nature, severity and attributions of the AEs. General guidelines are provided below.

In the event that trametinib and pembrolizumab need to be discontinued due to toxicity reasons, treatment with dabrafenib may continue at the discretion of the investigator until time of disease progression.

6.2.1 Dabrafenib +/- Trametinib Dose Modification Requirements for drug-related adverse events **Not Specified** in Subsequent Sections

CONFIDENTIAL

This document is confidential. Do not disclose or use except as authorized.

Table 6-2: Dabrafenib +/- Trametinib Dose Modification Requirements for drug-related adverse events Not Specified in Subsequent Sections

CTCAE Grade	Action and Dose Modification
Grade 1	
 • Continue study treatment at same dose level (no dose modification). • Monitor closely. • Provide supportive care according to institutional standards.
Grade 2 (Tolerable)	
 • Interrupt study treatment if clinically indicated. • Monitor closely. • Provide supportive care according to institutional standards. • When toxicity resolves to grade 1 or baseline, restart study treatment at current dose level.
Grade 2 (Intolerable) Grade 3	
 • Interrupt study treatment. • Monitor closely. • Provide supportive care according to institutional standards. • When toxicity resolves to grade 1 or baseline, restart study treatment reduced by one dose level. • If the grade 3 toxicity recurs, interrupt study treatment. • When toxicity resolves to grade 1 or baseline, restart study treatment reduced by another dose level.
Grade 4	
 • Interrupt study treatment. • Monitor closely. • Provide supportive care according to institutional standards. • Restart with study treatment reduced by one dose level once toxicity resolves to grade 1 or baseline. • If the grade 4 toxicity recurs, either permanently discontinue study treatment or, if the patient is clinically benefiting, discuss continuation of study treatment with the overall PI.

*If the AEs are thought to be due to one of the two agents, resumption of the other agents may be considered if the first agent is discontinued due to toxicities and treatment interruption is <21 days. Overall PI should be consulted for resumption of single agent. ** In the event of abdominal pain or suspected pancreatitis, amylase and lipase laboratory samples should be collected for confirmation of the diagnosis.
	

6.2.2 Dabrafenib + Trametinib Dose Modification Requirements for **Pyrexia**

- Pyrexia is defined as a body temperature equal to or above 38.5° Celsius or 101.3° Fahrenheit
- Pyrexia is an adverse event associated with dabrafenib. In a minority of cases, pyrexia was accompanied by symptoms such as severe chills/rigors, dehydration, hypotension, dizziness or weakness and required hospitalization.
- Subjects should be instructed on the importance of immediately reporting febrile episodes.
- Pyrexia accompanied by hypotension, dehydration, renal insufficiency and/or severe (grade ≥3) rigors/chills in the absence of an obvious infectious cause should be reported as an SAE.

CONFIDENTIAL

This document is confidential. Do not disclose or use except as authorized.

Table 6-2: Dabrafenib + Trametinib dose Modification and Management Requirements for Pyrexia

Event	Management Guideline	Dose Modification

Work up:
 
 • Clinical evaluation for infection and hypersensitivity, especially if pyrexia is complicated by rigors, severe chills, dehydration, etc. • Laboratory work-up (recommend include full-blood-count, electrolytes, creatinine, BUN, CRP, liver-function tests, blood and urine culture). 
Management:
 
 • Anti-pyretic treatment should be started immediately at the first occurrence. Anti-pyretic treatment may include acetaminophen (paracetamol), ibuprofen, or suitable anti-pyretic medication per institutional standards. • Oral hydration is encouraged in subjects without evidence of dehydration. Intravenous hydration is recommended if pyrexia is complicated by dehydration/hypotension. • In subject experiencing pyrexia complicated by rigors, severe chills, etc., which cannot be controlled with anti-pyretic medication, recommend oral corticosteroids be started. • Prophylactic anti-pyretic treatment is recommended after the 2nd event. 		

1st Event:
	
 • Clinical evaluation for infection and hypersensitivity • Laboratory work-up • Hydration as required • Administer anti-pyretic treatment if clinically indicated and continue prophylactic treatment 	
 • Interrupt dabrafenib. • Continue trametinib. • Upon recovery to baseline, restart dabrafenib at the same dose level. If fever was associated with dehydration or hypotension, reduce dabrafenib by one dose level.

2nd Event
	
 • Clinical evaluation for infection and hypersensitivity • Laboratory work-up • Hydration as required • Within 3 days of onset of pyrexia: 
 – Optimize anti-pyretic therapy. – Consider oral corticosteroids (i.e., prednisone 10 mg) for at least 5 days or as clinically indicated. 	
 • Interrupt dabrafenib. • Continue trametinib. • Upon recovery to baseline, restart dabrafenib at the same dose level. If fever was associated with dehydration or hypotension, reduce dabrafenib by one dose level.

CONFIDENTIAL

This document is confidential. Do not disclose or use except as authorized.

Table 6-2: Dabrafenib + Trametinib dose Modification and Management Requirements for Pyrexia

Event	Management Guideline	Dose Modification
Subsequent Events:	
 • Clinical evaluation for infection and hypersensitivity • Laboratory work-up • Hydration as required • Blood sample for cytokine analysis • Within 3 days of onset of pyrexia: 
 – Optimize oral corticosteroid dose as clinically indicated for recalcitrant pyrexia. – If corticosteroids have been tapered and pyrexia recurs, restart steroids. – If corticosteroids cannot be tapered, consult medical monitor. 	
 • Interrupt dabrafenib. • Continue trametinib. • Once pyrexia resolves to baseline, restart dabrafenib reduced by one dose level.^h • If dabrafenib must be reduced to <75 mg BID, permanently discontinue dabrafenib.

^h Dabrafenib should be reduced by one dose level after three episodes of pyrexia which cannot be managed by best supportive care and increasing doses of oral steroids. Escalation of dabrafenib is allowed if no episode of pyrexia is observed in the 4 weeks subsequent to dose reduction.
		

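### The pyrexia table in section 6.2.2 contradicts itself on dabrafenib reduction from the third episode and on when antipyretics and prophylaxis begin

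*Combined protocol and SAP*

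**What the plan says.** Section 6 opens by requiring that dose delays and modifications follow the criteria it lists. The pyrexia table in section 6.2.2 has a work-up and management header, three event rows (1st, 2nd, subsequent) with a management column and a dose column, and a footnote h.

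- **Dabrafenib, 1st and 2nd events.** Both rows say "Upon recovery to baseline, restart dabrafenib at the same dose level", with a one-level reduction if the fever came with dehydration or hypotension.
- **Dabrafenib, Subsequent Events row.** "Once pyrexia resolves to baseline, restart dabrafenib reduced by one dose level". The marker for footnote h stands at the end of this instruction.
- **Footnote h.** Dabrafenib should come down one level "after three episodes of pyrexia which cannot be managed by best supportive care and increasing doses of oral steroids". It adds: "Escalation of dabrafenib is allowed if no episode of pyrexia is observed in the 4 weeks subsequent to dose reduction".
- **Antipyretics.** Header: "Anti-pyretic treatment should be started immediately at the first occurrence". 1st Event row: "Administer anti-pyretic treatment if clinically indicated and continue prophylactic treatment".
- **Prophylaxis.** Header: "Prophylactic anti-pyretic treatment is recommended after the 2nd event". The 1st Event row, just quoted, speaks of continuing it. The 2nd Event row asks for antipyretic therapy to be optimised and does not mention prophylaxis.

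Trametinib is continued in every row. Section 6.2 sets the first dabrafenib step down from 150 mg BID as "150 mg QAM, 75 mg QPM".

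**The concern.** A mandatory table should give one answer for one patient. Here, someone reading the row and someone reading the footnote can restart the same patient at different dabrafenib doses after a third episode, and both can claim to have followed the protocol. The header and the 1st Event row likewise disagree on whether a first fever is always treated with antipyretics and on when prophylaxis starts.

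What is at stake is the care of a febrile patient on dabrafenib and, for the first conflict, the delivered dabrafenib dose in cohort 1, where the planned course of targeted therapy is only eight weeks. Pyrexia is a known and frequent toxicity of the dabrafenib and trametinib combination (section 2.2.2.4), so the table is likely to be used.

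**Working it through.** **Step 1. Row against footnote h.** Take a patient with a third episode, without dehydration or hypotension at any of the three.

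| Case | Subsequent Events row | Footnote h |
|---|---|---|
| None of the three episodes manageable | reduce | reduce |
| Third episode managed | reduce | condition not met |
| First two managed, third not | reduce | read literally, three unmanageable episodes have not occurred |

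The two texts agree in the first case and part in the other two. The row carries no condition of its own, and the table does not say which text governs.

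**Step 2. Header against event rows.** Prophylaxis cannot be continued at the first event if it is first recommended after the second. The 2nd Event row, where the header's rule should appear, is silent. For antipyretics, the header's instruction at first occurrence is unconditional, while the 1st Event row attaches a condition. Neither conflict changes a dose instruction, because the dose column is the same for events 1 and 2.

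**Step 3. Size of the dose conflict.** The plan states no figure to reproduce, so this is a bound.

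Inputs:
- Full dose: 150 mg BID = 300 mg/day (section 5.3.2).
- One level lower: 150 + 75 = 225 mg/day (section 6.2).
- Planned initial targeted therapy: 2 + 6 = 8 weeks = 56 days (study calendar, note a).

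While reduced, the difference is 300 − 225 = 75 mg/day, and 75/300 = 25%. Planned induction dabrafenib is 300 × 56 = 16,800 mg. If the patient restarts on day d, reduced under the row and at full dose under the footnote, the gap is 75 × (56 − d) / 16,800.

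| Restart day (assumed) | Gap in mg | Share of plan, no re-escalation | Share if re-escalated after 28 days |
|---|---|---|---|
| 14 | 75 × 42 = 3,150 | 18.8% | 75 × 28 / 16,800 = 12.5% |
| 28 | 75 × 28 = 2,100 | 12.5% | 12.5% |
| 42 | 75 × 14 = 1,050 | 6.3% | 6.3% |

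The restart days are assumptions. The sums take one reduction from full dose, and they leave out the days of interruption, which both readings require.

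**Step 4. How often.** Section 2.2.2.4 reports pyrexia at the 150/2 dose in 39/55 = 71% (Part C) and in 88% of the 150/2 group in dose escalation. Both figures count patients with any episode, in an earlier study and not within eight weeks. The documents give no rate or timing for third episodes, so the number of patients affected here cannot be computed.

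**The case against.** The strongest reply concerns the first conflict. Footnote h is marked on the very instruction it is said to contradict, and a marked footnote ordinarily qualifies its line. The management column of the same row speaks of recalcitrant fever and of optimising steroids, which fits the footnote. Nor does the footnote contain the word only. If it qualifies the row, there is one rule; if it is not exclusive, there is no strict contradiction. Section 6.2 also describes its contents as general guidelines and bases modification on the nature, severity and attribution of the event.

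This reading is reasonable and may be what was meant. But the table does not state it, the row read alone has no condition, and section 6 makes the criteria binding. The two readings still give different doses after a managed third episode. The reply also leaves the header and 1st Event row unreconciled. It can be said that immediacy is about timing and the condition is about indication, and that prophylaxis is merely recommended. Even so, continuing a treatment that has not yet been recommended makes no sense as written.

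The reply is right about consequence. Two of the three conflicts could alter dabrafenib exposure only indirectly, through recurrence, and the documents give no figure for that. The upper end of the dose gap needs a third episode resolved by day 14, after two earlier interruptions and recoveries.

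**Conclusion.** The table conflicts with itself on three points and should be reconciled. Only the row against footnote h changes a dabrafenib dose directly, in cohort 1 and from the third episode: 25% of the daily dose while reduced, or about 6% to 19% of planned induction dabrafenib for assumed restart days 42 to 14, and at most 12.5% if the dose is raised again after four fever-free weeks. The conclusion on the text needs no assumption; these sizes rest on the assumed days and on a single reduction from full dose.

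Three stronger readings are tempting and are not supported.

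- A reader might infer that exposure will differ by site. More than one site takes part, but nothing shows that sites would read the table differently.
- A reader might infer an effect on the clinical benefit rate or on the tumour-microenvironment results. The documents do not link a one-level reduction to either. The clonality and PD-L1 comparisons in section 13.5 use the pre-treatment and two-week samples, which a third-episode rule could reach only if all three episodes fell within the lead-in. No Simon design figure depends on this table.
- A reader might apply the 71% and 88% to the 25 patients of cohort 1. That would count any episode, whereas the dose instructions for the first two do not conflict.

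**What to change.** In section 6.2.2, reconcile the Subsequent Events row with footnote h so that one stated condition governs the dabrafenib reduction, and state whether each of the three episodes has to meet it. Reconcile the header with the 1st and 2nd Event rows so that the start of antipyretics and the start of prophylaxis each appear once, in the same terms. The investigator and drug-safety lead decide which rule applies; this review takes no position on that. The cost is a wording amendment to one table, with no change to sample size, endpoints or analysis.

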6.2.3 Dabrafenib +/- Trametinib Dose Modification for Drug-Related **Rash**

Rash is a frequent AE observed in patients receiving trametinib, dabrafenib, or the combination of both therapies.

Recommendations for supportive care and guidelines for dose modifications for rash are based on experience with other MEK inhibitors and EGFR inhibitors (Balagula *et al.*, 2010; Lacouture *et al.*, 2011).

The institutional standards for the management of skin-related AEs can differ from these guidelines. In this case, best clinical judgment should be applied and a consultation with the study overall PI may be required.

CONFIDENTIAL

This document is confidential. Do not disclose or use except as authorized.

Table 6-3: Dabrafenib +/-or Trametinib Supportive care and Dose Modification Requirements for Drug-Related Rash

CTCAE Grade	Adverse Event Management	Action and Dose Modification

Recommended supportive care:
 
 • Prevention: Promote sunscreen use and avoid unnecessary sun exposure, use alcohol-free emollient creams, topical steroids and antibiotics as needed. • Pruritic lesions: cool compresses and oral antihistamines. • Fissuring lesions: Monsel's solution, silver nitrate or zinc oxide cream. • Desquamation: thick emollients and mild soap. • Paronychia: antiseptic bath, local potent corticosteroids, antibiotics, surgery as needed. • Infected lesions: topical or systemic antibiotics. 		

Grade 1
 
 • 	
 • Initiate prophylactic and symptomatic treatment measures.¹ • Use moderate strength topical steroid.² • Reassess after 2 weeks. 	
 • Continue study treatment. • If rash does not recover to baseline within 2 weeks despite best supportive care, reduce study treatment by one dose level.³

Grade 2
 
 • 	
 • Initiate prophylactic and symptomatic treatment measures.¹ • Use moderate strength topical steroid.² • Reassess after 2 weeks. 	
 • Reduce study treatment by one dose level. • If rash recovers to ≤ grade 1 within 2 weeks, increase dose to previous dose level. • If no recovery to ≤ grade 1 within 2 weeks, interrupt study treatment until recovery to ≤ grade 1. • Restart study treatment at reduced dose level.³

Grade ≥3
 
 • 	
 • Use moderate strength topical steroids PLUS oral methyl-prednisolone dose pack.² • Consult dermatologist. 	
 • Interrupt study treatment until rash recovers to ≤ grade 1. • Restart with study treatment reduced by one dose level.^{3,4} • If no recovery to ≤ grade 2 within 21 days, permanently discontinue study treatment.

1. Rash prophylaxis is recommended for the first 6 weeks of study treatment. 2. Moderate-strength topical steroids: Hydrocortisone 2.5% cream or fluticasone propionate 0.5% cream. 3. Approval of overall PI is required to restart study treatment after >21 days of interruption. 4. Study treatment may be escalated to previous dose level if no rash is evident 4 weeks after restarting study treatment.
		

CONFIDENTIAL

This document is confidential. Do not disclose or use except as authorized.

6.2.4 Dabrafenib +/- Trametinib Dose Modification for **Hand-Foot Skin Reaction (HFSR)**

Table 6-4: Dabrafenib + /or Trametinib Dose Modification for HFSR

CTCAE Grade	Adverse Event Management	Action and Dose Modification
Grade 1^a	
 • Lifestyle changes recommended.^b • Initiate symptomatic treatment if clinically appropriate^c 	Continue study treatment at current dose level.
Grade 2	
 • Lifestyle changes recommended.^b • Initiate symptomatic treatment.^c 	
 • Interrupt study treatment until recovery to ≤ grade 1.^d • Recovery to ≤ grade 1 within 7 days: restart study treatment at previous dose level. • If no recovery to ≤ grade 1 within 7 days or ≥ 2nd occurrence: restart with study treatment reduced by one dose level.
Grade ≥3	
 • Lifestyle changes recommended.^b • Initiate symptomatic treatment.^c • Consult dermatologist. 	
 • Interrupt study treatment until rash recovers to ≤ grade 1.^d • Restart with study treatment reduced by one dose level.^e • If 3rd occurrence, discontinue study treatment permanently.

^a A full-body skin examination and removal of pre-existing calluses and keratotic skin is recommended prior to initiation of study treatment.

^b Life-style changes: (1) reduce exposure of hands and feet to hot water; (2) avoid traumatic activity including vigorous exercise especially in the first 4 weeks after start of study treatment; (3) avoid constrictive footwear; (4) avoid excessive friction on the skin when applying topical treatments; (5) wear thick cotton socks and gloves, and shoes with padded insoles.

^c Symptomatic treatments: (1) use moisturizing creams frequently and especially on hands and feet; (2) consider topical keratolytics: urea 20-40% cream, or salicylic acid 6%, or tazarotene 0.1% cream, or fluorouracil 5% cream; (3) erythematous areas: clobetasol propionate 0.05% ointment; (4) pain: topical lidocaine 2%, and/or systemic pain medication such as nonsteroidal anti-inflammatory drugs, codeine, and pregabalin.

^d Approval of overall PI is required to restart study treatment after ≥21 days of interruption.

^e escalation of study treatment to the previous dose level is allowed if no HFSR is observed in the 4 weeks subsequent to dose reduction.

6.2.5 Dabrafenib + Trametinib Dose Modification for **Squamous Cell Carcinoma**

Cutaneous squamous cell carcinoma (SCC) has been observed in patients treated with dabrafenib and the combination of dabrafenib and trametinib. These treatment-related SCC should be surgically removed according to institutional practice; dose modifications or interruptions of the study treatment are not required. Occurrence of SCC must be reported as an SAE.

CONFIDENTIAL

This document is confidential. Do not disclose or use except as authorized.

6.2.6 Dabrafenib +/- Trametinib Dose Modification for **Renal Insufficiency**

Cases of renal insufficiency have occurred in patients receiving the combination of dabrafenib and trametinib. Prior to start of study treatment, concomitant medications should be reviewed for the potential risk of inducing nephrotoxicity and, if so, should be modified if clinically possible.

Table 6-5: Dabrafenib +/- Trametinib Treatment Modification Requirements for Renal Insufficiency

Serum Creatinine Level	Management Guideline	Action and Dose Modification
Serum creatinine increase >0.2 mg/dL (18 mcmol/L) BUT ≤0.5 mg/dL (44 mcmol/L) above baseline	
 Recheck serum creatinine within 1 week. Serum creatinine increase >1 week: contact Overall PI. If pyrexia is present, treat pyrexia as per guidelines.^a 	Continue study treatment at the same dose level.
Serum creatinine increase >0.5 mg/dL (44 mcmol/L) OR >2 mg/dL (>177 mcmol/L)	
 Monitor serum creatinine ≥2-times per week. Hospitalization may be necessary if serum creatinine cannot be monitored frequently. If pyrexia is present, treat pyrexia per guidelines. Consult nephrologist if clinically indicated. Perform renal biopsy if clinically indicated, for example: 
 Renal insufficiency persists despite volume repletion. Patient has new rash or signs of hypersensitivity (such as elevated eosinophil count). 	
 Interrupt study treatment until serum creatinine recovers to baseline. Restart study treatment.^b
^a NSAIDs can induce renal insufficiency, especially in patients with dehydration; encourage oral fluids or consider IV fluids as clinically indicated. ^b Investigator may restart at either the same or a reduced dose level. Escalation of study treatment to previous dose level is allowed if another episode of renal insufficiency does not occur after 4 weeks of dose reduction. Consultation with the overall PI is required before restarting study treatment if there is evidence of thrombotic microangiopathy.		

CONFIDENTIAL

This document is confidential. Do not disclose or use except as authorized.

6.2.7 Dabrafenib +/- Trametinib Dose Modification for **Reduced Left Ventricular Ejection Fraction**

Decreases of the left ventricular ejection fraction (LVEF) have been observed in patients receiving trametinib. Therefore, ECHOs must be performed at intervals outlined in the Study Calendar. The same procedure (either ECHO or MUGA, although ECHO is preferred) should be performed at baseline and at Week 9.

Table 6-6: Dabrafenib +/- Trametinib Treatment Modification and Management Requirements for LVEF Decrease

Clinic	LVEF-drop (%) or CTCAE grade	Dose Modification
Asymptomatic	Absolute decrease of >10% in LVEF compared to baseline and ejection fraction below the institution's LLN.	
 • Interrupt study treatment and repeat ECHO within 2 weeks.^a • If the LVEF recovers within 4 weeks (defined as LVEF ≥LLN and absolute decrease ≤10% compared to baseline): 
 – Consult with the overall PI and request approval for restart. – Restart trametinib and dabrafenib (if cohort 1) at reduced doses by one dose level. – Repeat ECHO 2, 4, 8, and 12 weeks after re-start; continue in intervals of 12 weeks thereafter. • If LVEF does not recover within 4 weeks: 
 – Consult with cardiologist. – Permanently discontinue trametinib. – Resumption of dabrafenib (if cohort 1) may be considered after consultation with the overall PI. – Repeat ECHO after 2, 4, 8, 12, and 16 weeks or until resolution.
Symptomatic^b	
 • Grade 3: resting LVEF 39-20% or >20% absolute reduction from baseline • Grade 4: Resting LVEF ≤20%. 	
 • Permanently discontinue trametinib. Consult overall PI for continuation of dabrafenib (if cohort 1). Consult with cardiologist. • Repeat ECHO after 2, 4, 8, 12, and 16 weeks or until resolution.
^a If ECHO does not show LVEF recovery after 2 weeks, repeat ECHO 2 weeks later. ^b Symptoms may include: dyspnea, orthopnea, and other signs and symptoms of pulmonary congestion and edema.		

